Sample size estimates are based on the mean changes and standard deviations observed in our pilot study (Table 2). Assuming a two-sided alpha of 0.05 and standard deviations of change from baseline of $0.20 \text{ mg} \bullet \text{kg}_{\text{lbm}} \bullet \text{min}$ for gluconeogenesis and $0.50 \text{ mg} \bullet \text{kg}_{\text{lbm}} \bullet \text{min}$ for glucose production, a trial with 12 participants in each group will have 80% power to detect a difference between metformin and combination therapy of $0.24 \text{ mg} \bullet \text{kg}_{\text{lbm}} \bullet \text{min}$ in gluconeogenesis and in $0.60 \text{ mg} \bullet \text{kg}_{\text{lbm}} \bullet \text{min}$ in glucose production. Analyses within each group will have 80% power to detect a change from zero if the true change is ≥ 0.18 and $\geq 0.44 \text{ mg} \bullet \text{kg}_{\text{lbm}} \bullet \text{min}$ for gluconeogenesis and glucose production respectively. For

the secondary outcome of change in GLP-1 AUC after an OGTT, we will have $> 95\%$ power to detect the mean difference of 101 pg•min/ml. **Assuming a 25% attrition rate, we will recruit 16 in each group.**

Table 2: Mean and Estimated Rates of Gluconeogenesis and Glucose Production and Projected Effect Sizes*

	Baseline Mean (SD)	Follow-up Mean (SD)	Difference Mean (SD)	15% Decrease	20% Decrease
Gluconeogenesis (mg•kg _{lbm} •min)	1.78 (0.41)	1.73 (0.31)	0.05 (0.19)	0.27	0.36
Glucose Production (mg•kg _{lbm} •min)	2.93 (0.92)	2.67 (0.54)	0.27 (0.50)	0.44	0.59
Early intact GLP-1 AUC (pg•min/min)	137 (113)	238 (128)	101 (32)	-	-

*Data from pilot study in 5 youth with type 2 diabetes treated with metformin 1000mg twice daily for 3 months.

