This power analysis was performed with two-sided T tests to detect a between group difference of a 15% change in gluconeogenesis which would require 12 individuals per group. Our primary assumption is that there will be a 15% difference in gluconeogenesis between the two study arms. This assumption is underscored by the fact that metformin will not result in a change in gluconeogenesis *in vivo*^{24,26,27} but liraglutide will decrease rates of gluconeogenesis by 15%. This sample size is in keeping with previous studies assessing metformin effect using similar techniques to measure of gluconeogenesis^{24,25}. Nevertheless, we acknowledge that the delta difference and SD for change between two differently treated groups could be larger. Therefore, this pilot study will provide valuable preliminary information for the magnitude of the difference between intervention groups that would be crucial for a larger randomized placebo controlled trial.

Analysis of Primary and Secondary Outcomes

The primary outcome, the change in gluconeogenesis from baseline to 12 weeks, will be analyzed using an analysis of variance that compares the two randomized groups adjusting for baseline levels. Similar analyses will be performed for the secondary outcomes, using transformations or nonparametric tests as appropriate. Secondary regression analyses will adjust for the effect of other variables (such as fat mass, metabolite and hormonal concentrations etc.) on these changes.

Analysis of Exploratory Outcomes

Pharmacogenomic Variants of Metformin Response

Given the limited sample size, the proposed genetic aims are exploratory in nature. First we will use 9 previously-identified genetic variants (Table 1) to construct a genetic risk score, calculated as the sum of the risk alleles that the individual has for any of the variants. Metformin response will be assigned as a 15% change in gluconeogenesis from baseline (minimum clinically relevant effect size) for each individual^{26,91}. We will then compare this risk score in the metformin responders vs. non-responders. The genetic risk score based on these 9 variants associated with metformin response in adults will be analyzed as a single predictor, and not by individual variants. Since this approach may miss important variation in these genes, particularly given that the question of metformin response has been less well studied among African-Americans, we will also sequence the genes of interest in these individuals.

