We will use regression models to determine if this risk score predicts metformin response in terms of changes in rates of gluconeogenesis and metformin concentrations in serum and urine, after adjustment for genome-wide proportion of African ancestry (additional covariates will be evaluated for inclusion), with $p < 0.05$ considered statistically significant. Rare variants identified during targeted gene sequencing will be analyzed in a composite way, collapsed by gene and considered with a rare variant analysis tool (e.g. SKAT⁹²). While this analysis may have limited power, the identification

of additional variants in these genes among African-American youth will inform future larger studies. Additionally, we will determine whether adding the sum of the risk alleles as covariates modifies the statistical analyses for the outcomes in Aim 1 and Aim 2. The composite genetic risk score will be used to adjust the primary outcome analysis of change in gluconeogenesis to see if accounting for this variation influences our conclusions. These results will be evaluated using a likelihood ratio test comparing a regression model adjusted and unadjusted for the variant.

Gut Microbiome and Metformin

Statistical analysis will be performed using a variety of computer packages including XLstat, NCSS 2007, “R” and NCSS 2010. Alpha and beta diversity analysis will be conducted as previously described^{86-88,93} using Qiime (www.qiime.org). Significance reported for any analysis is defined as p<0.05.

Metformin Pharmacokinetics

Statistical analysis and non-linear mixed effect modeling will be performed using the “Phoenix WinNonlin”, an industry standard for non-compartmental analysis, pharmacokinetic/ pharmacodynamic modeling.

Multiple-site Studies

Eligible patients may be identified through CNMC but no enrollment, informed consent or study visits will occur at CNMC.

The primary IRB on record will be NIH IRB. A Federalwide Assurance for Human Subject’s Protection (FWA) for Children’s National Medical Center is FWA00004487 and for PBRC is FWA 00006218.

We will also utilize the Translational Research in Pediatrics Program (TRIPP), an established contractual agreement between CNMC and the National Institutes of Health Clinical Center (NIH CC). A Reliance agreement has been executed between NIH and CNMC.

Human Subject Protection

Informed Consent/Assent Procedures

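### The likelihood ratio test named for the genetic-score adjustment tests whether the score predicts the outcome, not whether adjustment changes the arm comparison

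*Combined protocol and SAP*

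**What the plan says.** All references are to the Combined protocol and SAP, Statistical and Power Analyses.

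- **Primary analysis** (Analysis of Primary and Secondary Outcomes): the change in gluconeogenesis "will be analyzed using an analysis of variance that compares the two randomized groups adjusting for baseline levels".
- **Score** (Pharmacogenomic Variants of Metformin Response): built from nine variants and "calculated as the sum of the risk alleles that the individual has for any of the variants". It is to enter as one predictor, not variant by variant.
- **Score and outcome** (same section): "We will use regression models to determine if this risk score predicts metformin response in terms of changes in rates of gluconeogenesis", at the 0.05 level.
- **Purpose of the adjustment**, given twice in that section: "we will determine whether adding the sum of the risk alleles as covariates modifies the statistical analyses for the outcomes in Aim 1 and Aim" (the last words point to the second aim); and the composite score "will be used to adjust the primary outcome analysis of change in gluconeogenesis to see if accounting for this variation influences our conclusions".
- **Criterion**: "These results will be evaluated using a likelihood ratio test comparing a regression model adjusted and unadjusted for the variant".

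The section gives no rule for comparing the arm estimate, its interval or its p-value between the two models. It specifies no score-by-arm interaction. It calls the genetic aims exploratory because the sample is small.

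**The concern.** Aim 1 and the primary analysis compare two randomized arms, so the conclusion that adjustment might influence is the arm difference. The stated criterion looks at something else. Two nested models that differ only by the score are separated by one hypothesis: that the score coefficient is zero. The arm coefficient is in both models and is never compared. The test therefore largely repeats the score-prediction regression already planned in the same section, and the question actually posed has no rule.

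What is at stake is the reading of a sensitivity analysis on the primary outcome. A significant test can go with an arm conclusion that has not moved. A non-significant test can go with one that has.

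**Working it through.** **The plan's own figures.** Sample Size Justification – Primary Study starts from "Assuming a two-sided alpha of 0.05 and standard deviations of change from baseline of" 0.20 for gluconeogenesis, with a detectable difference of 0.24. The standardized effect is 0.24/0.20 = 1.2. A two-sided two-sample t test with 12 per group has power 80.2%, and 12/(1 − 0.25) = 16 recruited per group. The plan's figures reproduce, so 24 completers is the size used below.

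**What each quantity measures.** Write M0 as change on arm and baseline, and M1 as M0 plus score.
- The likelihood ratio statistic is LR = N ln(RSS0/RSS1). It is a function of the score coefficient relative to its standard error.
- The shift in the arm estimate is, exactly, (arm estimate in M0) − (arm estimate in M1) = (score coefficient in M1) × (baseline-adjusted difference in mean score between arms). The second factor is chance imbalance, with mean zero under randomization, and LR does not reflect it.
- Adjustment also changes the standard error of the arm estimate, so its p-value can change with little shift in the estimate.

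This mismatch follows from the definitions and needs no assumed effect size.

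**How often the two disagree.** The effect of the score is not in the documents, so it is assumed and ranged. Other inputs: 12 per arm, residual SD 0.20, true difference 0.24, normally distributed score, chi-square reference with 1 df, 0.05 throughout.

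| Score effect per SD (assumed) | Test rejects | Treatment significance changes, given rejection | Test non-significant, given a change |
|---|---|---|---|
| 0 | 8% | 10% | 83% |
| 0.05 | 25% | 13% | 54% |
| 0.10 | 65% | 18% | 18% |
| 0.15 | 91% | 26% | 3% |

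These are simulated percentages. Repeat runs agree to within about two points. At 0.10 per SD the median shift in the arm estimate among rejecting trials is about 0.03, against the planned difference of 0.24.

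**Sensitivity to the set-up.** In the table, score variance is added to the 0.20. At 0.10 per SD the total SD becomes √(0.20² + 0.10²) ≈ 0.22. A second run held the total at 0.20 and drew allele counts from the Table 1 minor allele frequencies (minor alleles counted, variants taken as independent). With the score explaining 0, 10%, 30% or 50% of the variance:
- the test rejects in 7%, 38%, 84% and 99% of trials;
- treatment significance is unchanged in 89%, 86%, 83% and 80% of the rejecting trials;
- among trials where it changes, the test is non-significant in 82%, 35%, 6% and 0.3%;
- the mean shift in the arm estimate is never more than 0.001.

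**Size of the test under no score effect.** M1 has four coefficients, so N = 24 leaves 20 residual df and LR = 24 ln(1 + F/20). The chi-square cut-off 3.841 corresponds to F = 20(e^(3.841/24) − 1) ≈ 3.47. On 1 and 20 df that is exceeded in about 7.7% of trials. The t (F) test holds 5%.

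**The case against.** The strongest reply is that the plan does fit both models. It says the score will adjust the primary analysis and that the team will see whether doing so modifies the Aim 1 and Aim 2 analyses, so both arm estimates will exist. That is right. It makes the fix free, but it supplies no rule: the one criterion written down still does not use those estimates.

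Nor are the two things unrelated. At 0.10 per SD, treatment significance changes in 18% of trials with a significant test and in about 7% of those without, and roughly 83% of all changes fall where the test is significant. The failure in the other direction dominates only when the score has little or no effect; with no effect, a change occurs in about 4.5% of trials. This limits the practical harm but does not make the test a measure of influence on the conclusion.

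The excess rejection depends on implementation. The plan names no reference distribution, and in a Gaussian linear model the likelihood ratio is a monotone function of F, so an exact version exists. With 32 participants the chi-square version rejects in about 7.0%. The switch from the composite score to *the variant* is loose wording whose meaning can be recovered from the preceding text.

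A reader might infer that a significant test would be reported as genetics having altered the trial's conclusions. The documents do not say so: they set no reporting rule, and do not say the test is all that would be reported. A reader might also infer harm to the primary result. That does not follow, because the baseline-adjusted arm comparison, its alpha and its sample size stand apart from this exploratory step.

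**Conclusion.** The point holds as a mismatch between a stated purpose and its stated criterion. The likelihood ratio test answers whether the score is associated with the outcome given arm and baseline. It does not answer whether accounting for the score changes the arm difference or the conclusion drawn from it.

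That rests on the definition of the test. The size of the disagreement rests on assumed score effects. Over 0 to 0.15 per SD, between about three quarters and nine tenths of significant tests leave treatment significance unchanged. The share of real changes that the test misses runs from about 83% down to 3%. No single row should be quoted as the expected behaviour.

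The consequence is minor: an exploratory sensitivity analysis could be misread, and nothing confirmatory is touched.

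**What to change.** In Pharmacogenomic Variants of Metformin Response, replace the likelihood ratio sentence with three statements:

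1. The arm difference with its 95% CI will be reported side by side from the models with and without the composite score. Influence on the conclusions will be judged by the change in that estimate and its interval.
2. Any test of the score coefficient will be presented only as a test of score-outcome association, using the t (F) reference rather than chi-square.
3. The term added is the composite score, in place of *the variant*.

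If effect modification by genotype is what is meant, a score-by-arm interaction has to be stated separately, because neither the present test nor the side-by-side comparison addresses it.

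Items 1 to 3 cost nothing beyond the edit. The same two models are fitted to the same data, and the primary analysis and sample size do not change.

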Hypothesis: During meal absorption, combination therapy with liraglutide and metformin will be associated with higher GLP-1 and insulin concentrations than metformin alone.

Exploratory Aim 1: To identify in African-American youth with type 2 diabetes, known pharmacogenomic variants previously associated with metformin response in adults and determine the relationship of these variants with change in gluconeogenesis and metformin concentrations.

Hypothesis: The 9 known variants of pharmacogenomics response identified in adults (Table 1) will be detectable in African-American youth. A higher genetic risk score (worse risk) of known metformin pharmacogenomic loci will be associated with (a) lower serum and urine metformin concentrations and (b) a smaller delta change in rates of gluconeogenesis.

Exploratory Aim 2: To compare the composition and distribution of gut microbiota before and after metformin.

Hypothesis: The composition and distribution of gut microbiota will change after metformin intervention.

Exploratory Aim 2: Construct a pharmacokinetic-pharmacodynamic model based on plasma and RBC metformin concentrations, and treatment outcome response (including change in glucose production, gluconeogenesis, incretin concentrations).

Hypothesis: Metformin concentrations will correlate with treatment outcomes over the 3-month study period.

Background

Metformin

Metformin treatment alone is suboptimal in 50% of all youth and ~ 65% of African-American youth with type 2 diabetes¹²¹³. This low efficacy in children was unexpected, not only because of greater metformin efficacy in adults¹⁴, but also because during the 8 week run-in phase of the TODAY study (Treatment Options for type 2 Diabetes in Adolescents and Youth), more than 85% of youth, regardless of race, were able to maintain glycemic control on metformin therapy¹⁵. Consequently, the reasons underlying this secondary treatment failure with metformin in children remain to be elucidated but do not appear to be related to either stressor scores or poor compliance¹⁶. We postulate that metformin's durable treatment efficacy is suboptimal in youth, especially African-Americans, because it has only a modest effect on lowering gluconeogenesis (a prominent feature of type 2 diabetes in youth).

Targeting gluconeogenesis with metformin

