- a) The change in the gut microbial composition and distribution in African-American youth with type 2 diabetes after 12 weeks of metformin.

Metformin response and pharmacokinetic-pharmacodynamic model

- b) Construct a pharmacokinetic-pharmacodynamic model based on plasma and RBC metformin concentrations, and treatment outcome response (including change in glucose production, gluconeogenesis, incretin concentrations).

Study Design and Methods

Study Design

This is a pilot randomized parallel design study of African-American youth with type 2 diabetes who are not on insulin therapy, with two intervention arms (combination therapy with metformin and liraglutide, and metformin alone).

Participants enter 5-7 day drug-free run-in period prior to initial metabolic evaluation. Participants will be evaluated before and after 12 weeks of study drug(s).

Randomization

The NIH Clinical Center (CC) Pharmacy will perform block randomization stratified by sex. Randomization will be stratified by sex with a block size of 6. The randomization schedules will be constructed by an independent statistician and shared with the NIH CC Pharmacy. The PI and study staff will not view the randomization schedule *a priori*. Subjects will be randomized as they enter the protocol as follows: The PI or study staff will notify the NIH CC pharmacy of the eligible enrolled participant and the pharmacy will assign the intervention arm according to the predetermined randomization schedule. All participant data will be entered into a NIDDK RedCap® database and the participant will be randomized consecutively using the single randomization list maintained by the NIH CC Pharmacy.

Study Protocol

Figure 1 illustrates the study design in which there will be 5 study visits: Visit 1 (screening outpatient), Visit 2 (tracer inpatient), Visit 3 and 4 (follow-up outpatient) and Visit 5 (tracer inpatient). Eligible patients may be identified at CNMC but no study visits will occur at CNMC.

[figure not shown]

Figure 1 –Study Design: randomized 12-week two-treatment arm clinical trial

Visit 1: Screening Outpatient Visit

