To calculate substrate oxidation, indirect calorimetry (hood) will be performed for 30-45 minutes between 7-8am, and 1-2pm to measure oxygen consumption and carbon dioxide production rates.

e. Stool Sample

A research stool sample will be collected at home and brought to the visit or collected during the admission. The stool sample will be stored at 4C in a sterile plastic vial and processed within 24 hours of collection.

f. Side-effect Questionnaire

Questionnaires will be completed by the participants at the study visit (Appendix A)

g. Blood glucose monitoring

Blood glucose will be monitored with either fingerstick blood glucose twice daily (fasting and bedtime) or by using an FDA- approved continuous glucose monitoring device (CGM) (for example, the Dexcom® CGM System). The device will be used to monitor glucose in real-time, approximately every 5 minutes. The system consists of a small sensor, transmitter, and hand-held receiver. The small sensor, with a small needle attached, will be inserted subcutaneously. The transmitter, which is attached to the sensor, will send the measured glucose to the receiver. The sensor is changed per manufacturer recommendations. Participants will receive training on removing and replacing the sensor and education on the signs and symptoms of hyperglycemia see Appendix B. All CGM or glucometer supplies will be provided by the study team.

Visit 3 and 4: Follow-up Outpatient Visit

Participants will return to the NIH CC clinic for an outpatient follow-up visit. Visit 3 will occur between 4-5 weeks and Visit 4 will occur between 8-9 weeks. The procedures at Visit 3 and 4 will be identical, and are outlined as follows:

1. Blood glucose records and glucometers will be reviewed.
2. Pill and pen counts performed by the study staff.
3. Blood and urine samples will be collected for glucose and metformin monitoring (including hemoglobin A1c, metformin concentrations).
4. We will review medication adherence and tolerance and emphasize compliance with study visits.
5. A research stool sample will be collected at home and brought to the visit or collected during the admission. The stool sample will be stored at 4C in a sterile plastic vial and processed within 24 hours of receipt.
6. We will collect questionnaire to assess side effects after starting the medication or changing dose. The sample questionnaire is in Appendix A.

Visit 5: Final Tracer Study

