Fecal samples will be collected in sterile cryovials and stored at 4C for less than 24 hours. The sample will be transferred to -80C and stored until further analysis. This analysis will be performed in collaboration with [name] and [name]. After thawing of fecal sample, fecal DNA will be isolated for microbial compositional analysis using PowerSoil® DNA Isolation Kit. Amplicon sequencing using next generation technology (bTEFAP®) will be used to for microbial sequencing using Illumina MiSeq and HiSeq platforms technologies. In brief, the 16S universal Eubacterial primers 27F AGAGTTGATYMTGGCTCAG and 519R GTNTTACNGCGGCKGCTG will be utilized to evaluate the microbial ecology of each sample on the Illumina MiSeq with methods via the bTEFAP® DNA analysis service. A single-step 30 cycle PCR using HotStarTaq Plus Master Mix Kit (Qiagen, Valencia, CA) will be used under the following conditions: 94C for 3 minutes, followed by 28 cycles of 94C for 30 seconds; 53C for 40 seconds and 72C for 1 minute; after which a final elongation step at 72C for 5 minutes will be performed. Following PCR, all amplicon products from different samples will be mixed in equal concentrations and purified using Agencourt Ampure beads (Agencourt Bioscience Corporation, MA, USA). Samples will be sequenced utilizing the Illumina MiSeq chemistry following manufacturer's protocols.

The Q25 sequence data derived from the sequencing process will be processed using a pipeline (MR DNA, Shallowater, TX). Sequences will be depleted of barcodes and primers then short sequences < 200bp are removed, sequences with ambiguous base calls removed, and sequences with homopolymer runs exceeding 6bp removed. Sequences are then denoised and chimeras removed. Operational taxonomic units (OTU) will be defined after removal of singleton sequences, clustering at 3% divergence (97% similarity)⁸⁶⁻⁸⁹. OTUs will be taxonomically classified using BLASTn against a curated GreenGenes/RDP/NCBI derived database⁹⁰ and will be compiled into each taxonomic level into both “counts” and “percentage” files. Count files contain the actual number of sequences while the percent files contain the relative (proportion) percentage of sequences within each sample that map to the designated taxonomic classification.

Metformin Pharmacokinetics

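### The microbiome section calls any analysis significant at p<0.05 without multiplicity control; if taxa are tested one by one, some chance findings should be expected to carry that label

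*Combined protocol and SAP*

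**What the plan says.** Under Analysis of Exploratory Outcomes, the Gut Microbiome and Metformin paragraph lists software, says "Alpha and beta diversity analysis will be conducted as previously described", and closes with "Significance reported for any analysis is defined as p<0.05". It names no diversity index, test, taxonomic level, prevalence filter or number of tests, and it does not say whether p is raw or adjusted.

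Under Clinical and Laboratory Methods, Microbiome Analysis, sequences are clustered into operational taxonomic units at 97% similarity and classified. The results "will be compiled into each taxonomic level into both" count and percentage files.

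The hypothesis in the first of the two aims numbered Exploratory Aim 2 is: "The composition and distribution of gut microbiota will change after metformin intervention". The matching entry among the exploratory outcomes in Study Objectives is "The change in the gut microbial composition and distribution in African-American youth with type 2 diabetes after 12 weeks of metformin".

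The instruction "A research stool sample will be collected at home and brought to the visit or collected during the admission" appears for Visit 2 and again for Visits 3 and 4. Visit 5 repeats the Visit 2 procedures. Each participant can therefore supply four samples, which allows three comparisons with baseline.

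The neighbouring pharmacogenomic aim limits its tests: the nine-variant risk score "will be analyzed as a single predictor, and not by individual variants".

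**The concern.** The threshold is stated, but the set of tests it governs is open. The plan creates a separate variable for each taxon at each level and then applies a per-test 5% rule to whatever is analysed. Used on individual taxa, that rule attaches the word significant to a predictable share of unchanged taxa.

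The aim names no taxon, index or direction in advance, so a reader of the results could not tell a chance taxon from a real one. The Background presents this as the first such evaluation in African-American youth and hopes it will inform a larger study of the gut as a metformin target. A list of taxa that arose by chance could misdirect that work. The primary and secondary outcomes are not touched.

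**Working it through.** **Plan's own figure.** The microbiome section has no sample size, power or test count to reproduce; its only figure is the 0.05 threshold. The primary-outcome sample size (12 evaluable per group, 12/(1 - 0.25) = 16 recruited) matters here only for the number of participants who might contribute stool: 12 for one evaluable arm, 24 for both, 32 for all recruited.

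**Inputs.** Per-test threshold 0.05 (Gut Microbiome and Metformin). Number of tests m: not given, so a range is assumed.

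**Step 1: independent tests, no true change.** Expected false positives = 0.05 × m. Chance of at least one = 1 - 0.95^m.

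| m | Expected false positives | Chance of at least one |
|---|---|---|
| 2 | 0.05 × 2 = 0.10 | 1 - 0.9025 = 9.8% |
| 5 | 0.05 × 5 = 0.25 | 22.6% |
| 20 | 0.05 × 20 = 1 | 64% |
| 50 | 0.05 × 50 = 2.5 | 92% |
| 100 | 0.05 × 100 = 5 | 99.4% |

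The first two rows stand for a plan that tests only a few diversity measures; the others stand for taxon-by-taxon testing. Testing every post-baseline visit would triple m: 20 taxa at three visits make 60 tests and 0.05 × 60 = 3 expected false positives.

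**Step 2: correlated taxa.** Paired t-tests were simulated with no true change for 12, 24 and 32 participants, with a common correlation between taxa and 400 runs per setting.

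- At 100 taxa the average number of false positives stayed near 5 (4.4 to 5.3) whatever the correlation.
- At 100 taxa the chance of at least one was about 94-96% at correlation 0.3 and about 63-67% at correlation 0.6.
- At correlation 0.6 the chance was about 33-39% with 20 taxa and 83-86% with 300.

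Correlation therefore bunches the false positives into fewer trials without reducing their average number.

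**Step 3: sparse taxa.** With a signed-rank test and 24 participants, the null rejection rate was about 1% for a taxon present in 10% of samples, 3.7% at 20%, and about 5% at 50% or more. The 5% figure therefore applies to adequately prevalent taxa; 0.05 × m overstates the count when many taxa are rare.

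**Step 4: effect of the remedy.** In the Step 2 simulations, Benjamini-Hochberg at 5% brought the chance of reporting any taxon to about 2-6% in every setting. Only zero or positive correlations were tried.

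**The case against.** The strongest reply is that the plan never says taxa will be tested one at a time. The only analyses it names are alpha and beta diversity, and the laboratory section describes a data pipeline, not a set of tests. That is correct. Taxon testing is an inference from the per-level files and from a rule worded to cover all analyses. If only two to five diversity tests are run, the inflation is modest.

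A reader might infer that false positives are guaranteed, or that the hypothesis of a changed microbiota is almost certain to be declared supported when nothing has changed. The documents support neither reading. The number of tests is unknown, 20 independent taxa give 64% and not certainty, and correlation lowers that further. The hypothesis concerns the community as a whole, and no rule says that a single taxon would confirm it.

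Two further points stand in part. The diversity methods are given by citation, and what those sources do about multiplicity cannot be seen here. The outcome is exploratory in a pilot, which lowers the importance; but it does not make an unadjusted label of significance sound when the plan chooses to use that label. A strict false-discovery cut-off could also hide most leads in a sample this small, so unadjusted results should stay visible.

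**Conclusion.** The point holds in a limited form. The plan states a 5% threshold for any microbiome analysis, generates data on every taxon at every level, and contains no multiplicity control for them. If taxa are tested individually, about 5% of adequately prevalent ones would be called significant with no true change.

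The size rests on three assumptions: that individual taxa are tested, how many there are, and how strongly they are correlated. The chance of at least one false finding runs from about 10-23% for a handful of diversity tests, through 64% for 20 independent taxa, to 99% for 100 independent taxa or 63-67% for 100 strongly correlated ones. Severity is low, because only the exploratory microbiome conclusions are affected.

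**What to change.** In the Gut Microbiome and Metformin paragraph, replace the closing rule with the following:

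- Name one alpha-diversity and one beta-diversity measure, each with its test, comparing baseline with 12 weeks, and keep p<0.05 for those two.
- For taxon-level tests, report Benjamini-Hochberg q-values, either at one taxonomic level named in advance or pooled across all levels tested. Adjusting separately within each of several levels would leave the multiplicity across levels uncontrolled.
- Use the word significant for a taxon only at a false-discovery rate of 5%.
- Show unadjusted p-values as well, labelled hypothesis-generating.

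This takes a few sentences and standard software, with no new samples or participants. The cost is that fewer taxa, possibly none, will be called significant in a pilot with about 24 completers. Keeping the unadjusted values visible preserves the leads for a later study.
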